7.5.3 Nutritional and Physical Activity Assessments

Fruit and vegetable consumption will be measured with National Institutes of Health's Eating at America's Table study¹⁰⁸. Participants will be asked various questions regarding the frequency and quantity of various food groups in the past month. A total score is calculated by converting

quantity to a standard scale for each food category, multiplying by the frequency, and summing. This questionnaire will be implemented at baseline and follow-up visits (See Appendix E and F).

Participants will wear the Fitbit on their non-dominant hand for seven days and a minimum of four days with ten hours per day of wear time required for analyses. Fitbits have been determined to be reliable and valid measures of physical activity¹⁰⁹. Established cut-points will be used to determine minutes of moderate to vigorous physical activity¹¹⁰. Average daily physical activity will be normalized and reported as minutes per week of moderate to vigorous physical activity. The Fitbits will also capture process variables, such as heart rate and steps.

7.6 BWL intervention

All patients enrolled will receive a 6 month remotely delivered behavioral lifestyle intervention primarily through a web-based platform. For purposes of this study, lifestyle coaches will be supplied by Johns Hopkins. The coaches are trained in both behavioral weight loss principles and motivational interviewing will have access to self-monitoring data through the platform, allowing them to review multiple aspects of adherence to dietary and physical activity behaviors as well as weight loss progress. To tailor the intervention to breast cancer survivors, we have provided the coaches with comprehensive training regarding breast cancer subtypes, types of therapy patients have received and might still be taking (e.g., hormonal, anti-HER2 agents), expected side effects from prior or ongoing therapy (e.g., fatigue, neuropathy, lymphedema, hot flashes), scheduled standard clinic visits and tests, and symptoms disconcerting for a recurrence. Coaches will discuss additional dietary and physical activity recommendations that are standard for breast cancer patients such as moderation of alcohol intake. Patients are provided with modules of recommended exercises per American College of Sports Medicine and American Cancer Society recommendations, particularly in reference to lymphedema prevention¹¹¹.

The participants will have access to a web-based platform which provides support for lifestyle counseling in behavioral methods of weight management; a summary of the support and methods will be given at the first/in-person visit with the weight loss coach. Participants in this group will be encouraged to record diet, exercise, and weight on this web-based platform. Web-links to health related websites may also be left by the coach. These participants will receive usual medical care from their providers (i.e., oncologists and primary care physicians). Providers will support and encourage participants to be actively engaged in the lifestyle counseling intervention.

7.6.1 Goals

The goals of this intervention (from months 3-6) are to induce weight loss of 5% or more by adding pharmacotherapy to behavioral weight loss interventions in women whom are unable to achieve 5% weight loss with lifestyle modifications alone.

7.6.2 Description and delivery of the intervention

Participants in this group will receive a behavioral weight loss intervention consisting of:

- Teleconferencing and/or phone calls by coaches (see frequency of contacts below);
- A lifestyle counseling curriculum delivered via the web (hard copies also provided as requested); and

• Online tools for behavioral self-monitoring.

7.6.3 The lifestyle curriculum:

The lifestyle curriculum consists of learning materials which will be provided in a binder and can be provided electronically. The curriculum focuses on self-monitoring, behavioral strategies for modifying eating behavior and increasing physical activity, stimulus control, social support, problem solving, and cognitive restructuring. Goal setting is also a key component of the intervention.

7.6.4 Self-Monitoring

All participants are advised to:

- Record weight at least once each week.
- Record daily: minutes of moderate to vigorous physical activity (MVPA) in bouts of 10 minute bouts or more, and all food and beverages consumed daily using the smartphone application or website.

7.6.5 Participant contact

Participants receive teleconferencing/telephone calls weekly for 3 months and monthly thereafter from lifestyle coaches to encourage completion of learning materials modules, to reinforce key learning points, and to encourage logging and provide feedback on weight, food intake, and exercise tracking. Calls will be each week for months 1-3, once a month for months 4-6. Each call will be approximately 30-45 minutes long. For all participants, coaches will also review and/or inquire about any new symptoms (weekly during months 4-6) and adherence if they are assigned to the arm with the pharmacotherapy. If symptoms are reported, the coach will notify the physician on study and the patient may be contacted by the physician for further evaluation.

7.6.6 Assessment of adherence

Adherence to intervention for participants will be based on completion of coach contacts and modules, and online self-monitoring of weight, food intake, and exercise. Additionally, patients on the SLOW-BWL arm will complete a drug diary log during the one-month long titration (APPENDIX G). Patients will e-mail their logs to the study team for review.

7.6.7 Provider role

At routine medical visits, these participants will be encouraged by their oncologist to actively engage in the intervention. Providers will receive a report that provides a snapshot of their patient's progress and that provides key behavioral recommendations to reinforce.

7.6.8 Description of BWL Intervention

Month 1-3		
Frequency	Weekly	Entire duration of study
Mode	Teleconferencing or phone calls	Automated weekly weight entry

Month 4-6		Entry of diet and exercise
Frequency	Monthly	
Mode	Teleconferencing or phone calls	

The SLOW-BWL group will have the addition of Contrave to BWL from Month 4-6

7.6.9 Weight Goals and Behavioral Recommendations

Remote-Support Weight Loss Intervention					
Weight Loss Goal	Minimum 5% weight loss, individually tailored				
Behavioral Recommendations					
Total Calorie Intake	Active weight loss				
	$1200 \text{ kcal/d if} \leq 170 \text{ lbs}$				
	1500 kcal/d if > 170 lbs and < 200 lbs				
	1800 kcal/d if > 200 lbs and < 270 lbs				
	2200 kcal/d if > 270 lbs				
	Maintaining weight loss				
	1500 – 1900 kcal/d				
Dietary Pattern	Option 1: DASH diet				
	7-12 servings of fruits/vegetables				
	2-3 servings of low fat dairy				
	Low sodium				
	\leq 25% of calories from fat				
	Option 2: Mediterranean diet				
	Daily consumption of vegetables, fruits, whole grains				
	and healthy fats				
	Weekly intake of fish, poultry, beans and eggs				
	Moderate portions of dairy products				
	Limited intake of red meat and alcohol				
Physical Activity	Build to ≥ 180 minutes/week of moderate intensity physical				
	activity in bouts ≥ 10 minutes in length				
Self-Monitoring Recommenda	tions				
Weight	Weekly				
Calorie counting	Daily				
Physical activity	Daily				
Mode	Online behavioral tracking of above behaviors				

7.7. Concomitant and Supportive Therapy

In general, concomitant medications and therapies deemed necessary for the supportive care and safety of the subject are allowed, provided their use is documented in the medical records. Any

^{*}From months 4-6, for any patients in either arms who are struggling with weight loss (i.e. motivation, behavioral concerns, weight regain etc.), an additional 2 "booster" visits can be scheduled through teleconferencing sessions.

changes in medications during the study must be clearly documented in the study records. The administration of any other therapies intended to treat the breast cancer, with the exception of trastuzumab (Herceptin®) and endocrine treatment (i.e., aromatase inhibitor) is NOT permitted. As noted, changes in endocrine treatment during study participation should be avoided. The initiation of or changes to any ongoing medications listed in Section 6.2.4 should also be avoided, if possible.

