6.2 Exclusion criteria

- 6.2.1 Serious/uncontrolled medical condition at the discretion of the Protocol Chair/designee likely to hinder accurate measurement of weight or any condition for which weight loss is contraindicated or would affect adipokine and inflammatory markers (e.g. active malignancy, end stage renal disease on dialysis, cirrhosis, autoimmune disease, adrenal disease, uncontrolled hypertension, seizure disorder, and history of bariatric surgery)
- 6.2.2 Pregnant or nursing within past 6 months, or plans to become pregnant in the next year

- 6.2.3 Currently enrolled or planning to enroll in a weight loss program (e.g. Weight Watchers, Jenny Craig, Nutrisystem and Medifast) or to take a chronic weight loss medication.
- 6.2.4 Diabetes on insulin or sulfonylureas within the past 3 months
- 6.2.5 Unstable psychiatric disorder or bulimia/anorexia nervosa
- 6.2.6 Alcohol, nicotine or substance abuse; or undergoing abrupt discontinuation of alcohol, benzodiazepine, barbiturate or anti-epileptic drug
- 6.2.7 Use of the following medications are excluded:
 - Tamoxifen
 - MAO inhibitors (must be >14 days from discontinuation)
 - Thyroid medication use unless on stable doses for at least the past 3 months
 - Buproprion containing products or opiate agonists (must be >14 days from discontinuation)
 - Medications that cause weight loss (e.g., lorcaserin, phentermine, orlistat, Qsymia, Contrave) within the past 3 months
 - Medications that are likely to cause weight gain or prevent weight loss (e.g., corticosteroids, lithium, olanzapine, risperidone, clozapine, oral contraceptive pills, hormone replacement therapy) within the past 3 months. NOTE: An exception to this is that SSRI's and SNRI's are allowed if participant has been on stable doses for at least 3 months (if discontinued, a washout of 2 weeks from prior SSRI/SNRI use is required).
 - Medications that may affect adipokine or inflammatory markers (e.g., metformin, glitazones, steroids, ACE inhibitors, beta blockers and statins) unless on stable doses ≥3 months prior to registration (if discontinued, a washout of 2 weeks from prior use is required). Concurrent NSAIDs are allowed if use is limited to <3 times per week; chronic NSAIDs are permitted on study only if use has been ≥3 times per week for at least 3 months prior to registration and is expected to continue.

NOTE: No medication should be discontinued without guidance of the prescribing provider.

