7.2 Determination of Eligibility

After eligibility is established by the coordinator during the screening call, the study staff will register participants, assign a study number, and schedule an in-person baseline visit. Participants will not begin protocol-specified treatment until eligibility is confirmed by the study staff at the baseline visit. Participants who sign a consent form, but do not initiate protocol intervention for any reason, will be replaced and will not count towards our accrual goal.

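### Section 7.7 cites criterion 6.2.4 where the drug list is 6.2.7, and no rule ties the first Contrave dose at week 9 to the 2-month medication review

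*Combined protocol and SAP*

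**What the plan says.** Section 7.7 sets the on-study drug rules. In general, "concomitant medications and therapies deemed necessary for the supportive care and safety of the subject are allowed", provided they are documented. The paragraph bars other breast cancer treatments, apart from trastuzumab and endocrine therapy. It adds that "changes in medications during the study must be clearly documented in the study records", and then: "The initiation of or changes to any ongoing medications listed in Section 6.2.4 should also be avoided, if possible".

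Criterion 6.2.4 reads "Diabetes on insulin or sulfonylureas within the past 3 months". The medication list is 6.2.7. Among its entries are "MAO inhibitors (must be >14 days from discontinuation") and "Buproprion containing products or opiate agonists (must be >14 days from discontinuation"). It also lists "Medications that cause weight loss (e.g., lorcaserin, phentermine, orlistat, Qsymia, Contrave) within the past 3 months".

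On timing, section 7.2 states: "Participants will not begin protocol-specified treatment until eligibility is confirmed by the study staff at the baseline visit". Section 7.3.2 also places confirmation of eligibility at the baseline visit. The Summary, 7.3 and 13.1 then start Contrave at week 9 in every woman who has lost less than 5%. Section 7.3.3 lists a review of current medications at the 2-month visit, and 7.5.1 says medications are asked about at each visit. The study calendar in section 8 marks current medications at screening and baseline only.

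**The concern.** Section 5.9 describes Contrave as bupropion combined with an opioid antagonist. The protocol keeps users of MAO inhibitors, bupropion products and opiate agonists out at entry, but the drug itself comes about two months later. Over that interval, the rule that should discourage starting such drugs points to a different criterion, and the rule that starts Contrave looks only at weight. A woman prescribed an opiate agonist in week 6, for example, would meet every written condition for Contrave at week 9. What is at stake is the safety of that woman. The primary analysis is not at stake.

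**Working it through.** **1. The cross-reference.** Section 7.7 speaks of ongoing medications that are listed. Criterion 6.2.4 is a single diabetes criterion, and users of its two drug classes are already excluded, so no eligible woman has an ongoing 6.2.4 drug to change. The sentence fits 6.2.7, which is a list with stable-dose and washout conditions. Taken literally, 7.7 discourages starting insulin or a sulfonylurea and is silent on the three classes. Its general permission for necessary medication then applies to them.

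**2. From eligibility to first dose.**

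| Step | Where | Condition on other drugs |
|---|---|---|
| Eligibility confirmed | 7.2, 7.3.2 (baseline) | 6.2.7 applies |
| Weeks 1 to 8, BWL alone | 7.7 | Caution cites 6.2.4; changes documented |
| 2-month visit | 7.3.3, 7.5.1 | Medications reviewed; no action stated |
| Same visit | Section 8 calendar | Medications not marked |
| Contrave starts | Summary, 7.3, 13.1 | None; weight loss below 5% only |

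The limits of more than 14 days in 6.2.7 name no reference date. As entry criteria they are checked at baseline, about 8 weeks (56 days) before the first tablet.

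**3. The design figures.** Section 13.1 stops if 1 or fewer of 15 women respond and rejects the null if 7 or more of 30 do, with rates of 10.9% and 29%. With X1 and X2 independent Binomial(15, p), the exact rejection probability is the sum over x = 2 to 15 of P(X1 = x) × P(X2 ≥ 7 − x).

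- p = 0.109: 0.0378 (plan: 5% limit).
- p = 0.29: 0.8006 (plan: 80%).

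The plan's figures reproduce, and neither depends on the drug rules.

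They would matter once women are withheld from Contrave, because 13.4 limits the ITT population to SLOW-BWL women who receive any of it. If withheld women were not replaced, with the cutoff kept at 7 and the shortfall in the second stage (X2 with 14 or 13 women):

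| Treated | Alpha at 10.9% | Power at 29% |
|---|---|---|
| 30 | 0.038 | 0.801 |
| 29 | 0.032 | 0.772 |
| 28 | 0.027 | 0.739 |

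**4. What a washout does to exposure.** These figures measure the cost of the fix; they do not measure the gap. Assumptions: day 1 is the first day of BWL; month 6 is 26 weeks, or 182 days; the interacting drug stops on the day of the visit; and more than 14 days means a first dose 15 days later. Section 7.4.1 lets the weight be taken up to 14 days after the 8 weeks end, so the visits considered are days 57 and 70 (56 + 14).

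- Day 57, no delay: 182 − 57 + 1 = 126 days = 18.0 weeks. With washout, first dose day 72: 182 − 72 + 1 = 111 days = 15.9 weeks.
- Day 70, no delay: 182 − 70 + 1 = 113 days = 16.1 weeks. With washout, first dose day 85: 182 − 85 + 1 = 98 days = 14.0 weeks.

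The Summary promises at least 16 weeks. If the month-6 weight is taken 14 days late (day 196), exposure after washout is 125 days (17.9 weeks) or 112 days (16.0 weeks).

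**5. Extra enrolment.** At the planned 55% SLOW-BWL share, replacing one withheld woman needs 1 / 0.55 = 1.8 more enrolled.

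**The case against.** The strongest reply is that the protocol is not blind to other drugs. Medications are asked about at every visit, including the 2-month visit, and changes must be recorded. Section 7.12 names the need for a therapy that the study does not permit as a reason for withdrawal. Section 7.11 ends the intervention on five listed criteria, only one of which mentions investigator judgment. A reader can see that 7.7 means 6.2.7, and a prescriber may well check for interactions.

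Most of this stands and limits the point. A reader might infer that nobody looks at medications before Contrave; 7.3.3 and 7.5.1 say otherwise. A reader might also infer that the stopping rules rest on discretion alone; the wording of 7.11 and 7.12 does not support that. Checks after the first dose are not confined to drug logs and symptoms either: 7.3 mentions monthly in-person visits, though its wording leaves unclear who attends, and 7.5.1 would bring a medication question to any such visit.

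These provisions do not supply the missing link. Section 7.12 concerns leaving the study, whereas the natural response here is to withhold Contrave and continue BWL, as 7.3 and 10.2.6 already do for intolerance. Whether 7.12 even reaches these drugs is uncertain, because the faulty reference means 7.7 never says they are disallowed on study. The calendar also disagrees with 7.3.3 on whether the week-9 review takes place.

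The week counts are approximate. Section 7.3.3 allows follow-up visits within 8 weeks of the assessment date, 13.1 has drug shipped to the home, and the table in 7.6.8 places Contrave in months 4 to 6. Actual starts could be later than those used here.

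**Conclusion.** The point holds. Section 7.7 cites the wrong criterion, and no text makes the first Contrave dose depend on the 2-month review or ties the 14-day limits to that dose. It should be fixed for patient safety.

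Its reach is narrow: women who start an MAO inhibitor, a bupropion product or an opiate agonist after baseline, and who are harmed only if the review is missed or not acted on. The documents give no rate for this, and none is assumed.

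A reader might go further and infer a flaw in the sample size or error rates. The documents do not support that: alpha of 0.038 and power of 0.80 follow from 13.1 whatever the drug rules say. The lower powers in the working arise only if women are withheld and not replaced.

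**What to change.** 1. In 7.7, replace the reference to 6.2.4 by *Sections 6.2.4 and 6.2.7, apart from Contrave given under this protocol*. The exemption is needed because 6.2.7 itself names Contrave. Add that MAO inhibitors, bupropion products and opiate agonists are not to be taken while on Contrave; if one is needed, Contrave is stopped, the Protocol Chair is told, and BWL continues.
2. In 7.3 and 13.1, state that Contrave is dispensed only if the 2-month medication review shows that the last use of any of these drugs was more than 14 days before the first dose. Otherwise Contrave is delayed or withheld and BWL continues.
3. In the study calendar, mark current medications at week 9.
4. In 13.1 and 13.4, state that SLOW-BWL women never dosed are reported separately and that accrual continues until 30 women have received Contrave. This keeps the exact alpha and power as designed.

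The cost is a few sentences, one corrected reference and one calendar mark. No visit is added. A woman who needs a full washout starts about 15 days late and may fall short of 16 weeks of drug by month 6 (15.9 or 14.0 weeks in the two cases above). Each woman never dosed adds about 1.8 to enrolment. Clinical details of stopping and restarting are for the sponsor's clinicians.

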7.8 Discontinuation and withdrawal of subjects

Participants who discontinue the study early will be asked to complete the next planned assessment at the time of discontinuation, if feasible and acceptable to the patient. All reasons for discontinuation of therapy should be documented clearly in the medical record.

7.11 Discontinuation of intervention

The intervention will continue for the planned 6 months except in patients who fulfill one or more of the following criteria:

- Diagnosis of new or recurrent intraductal or invasive breast cancer while on therapy where a change in treatment is planned.
- Intercurrent illness or change in the patient's condition that renders the patient unacceptable for further treatment in the judgment of the principal investigator (PI).
- Pregnancy
- Lack of compliance with treatment assignment.
- Patient request to discontinue protocol.

7.12 Withdrawal from Study

The reasons for withdrawal from the study include:

- Subject withdraws consent.
- Subject needs treatment not allowed in the study.
- Study is lost to follow-up.
- Study is canceled for any reason.

7.13 Additional Information

Participants who complete the study will be gifted the Fitbit and weight scale in appreciation of their time at the final study visit. Participants will also be offered parking vouchers at the end of each study visit, if applicable. Additionally, for patients who have completed the study and would like to continue weight management care within Johns Hopkins, the team will provide referrals to the Digestive Weight Loss Center (at Green Spring Station, Sibley Memorial Hospital or Johns Hopkins Hospital). This information will be included in the informed consent document.

8. STUDY CALENDAR

D. I	Screening call	Baseline	Follow-Up Visits ##	
Procedure	for eligibility	Visit ##	Week 9	Month 6
Clinical & Physical Assessments:		•	,	,
Consent		X		
Questionnaires		X		
History	X			
Physical exam		$X^{\#}$		
Current medications	X	X		
Performance status		X		
Weight Loss History	X			
Vitals		X	X	X
Up to date screening	X			
mammography within one year	Λ			
BMI Calculation	X*	X	X	X
Anthropomorphic Measurements:				
Height	X*	X		
Weight	X*	X	X	X
Research Correlates:				
Fecal sample		X	X	X
Serum pregnancy test (if age <60)		X		
Lipid panel, Hba1c		X	X	X
Purple research tube		X		
Red/gray research tube		X	X	X
Research Intervention:		•	·	
Patient Reported Outcomes		X	X	X
Provide Fitbit**		X		
Coaching (BWL intervention)***		X	X	X
Provide weight scale		X		

^{*}If greater than 3 months since last documented height and weight in electronic health record, will use patient reported most recent height and weight to determine eligibility based on BMI. However, BMI measured at baseline will serve as first data point.

^{**}Participants will wear the Fitbit on your non-dominant hand for 7 days and a minimum of 4 days with 10 hours per day of wear time.

^{***}Participants will communicate with their coach by phone. The coach will reach out to the participants at the baseline visit, and will provide weekly calls and emails the first 3 months. The last 3 months, participants will receive monthly calls and emails.

[#] Physical exam: may be performed and documented up to 3 months prior to baseline visit by a coinvestigator or provider within the institution. Or physical exam may be performed at or after baseline visit (but before initiation of the behavioral intervention)

Baseline visits should occur within 8 weeks of screening visit. Follow up visits should occur within 8 weeks of assessment date.

NOTE: Additional standard of care tests may be performed at the discretion of the treating investigator as clinically indicated. The schedule should be followed as closely as is realistically possible; however, the schedule may be modified due to problems such as scheduling delays or conflicts (e.g., clinic closure, poor weather conditions, vacations, etc.) with the guidance of the PI/designee, as appropriate, and will not be reportable as a deviation unless the endpoints of the study or subject safety are affected.

In order to minimize the need for research-only in-person visits, telemedicine visits may be substituted for in person clinical trial visits or portions of clinical trial visits where determined to be appropriate and where determined by the investigator not to increase the participants risks. Prior to initiating telemedicine for study visits the study team will explain to the participant, what a telemedicine visit entails and confirm that the study participant is in agreement and able to proceed with this method. Telemedicine acknowledgement will be obtained in accordance with the Guidance for Use of Telemedicine in Research. In the event telemedicine is not deemed feasible, the study visit will proceed as an in-person visit. Telemedicine visits will be conducted using HIPAA compliant method approved by the Health System and within licensing restrictions.

